2 STUDY DEVICE DESCRIPTION

The Study Device ("Device") is intended to aid healthcare providers in diagnosing Autism Spectrum Disorder (ASD) for children \geq 18 months of age and $<$ 72 months of age who are at risk for developmental delays based on a parental or healthcare provider concern.

The device is not intended for use as a stand-alone diagnostic device. It is intended to be used in conjunction with the clinical presentation of the patient.

The Device comprises of the following:

- A caregiver facing mobile application (Cognoa Research App)
- A Video Analyst Portal
- Healthcare Provider Assessment
- Underlying machine learning algorithm that drives the Device outputs ("Algorithm")

The Algorithm operates on information and data from three modules, that serve as data input.

Device Module	Module Description	Delivery System
Module 1 - Caregiver Assessment	Answers to questions on key developmental behaviors (by age group), provided by the child's caregiver.	Caregiver responses will be submitted via Cognoa Research App
Module 2 - Patient Video Analysis	Information provided by trained video analyst who reviewed videos of the child's natural play, communication, and social behavior at home, provided by the child's caregiver.	Caregiver will submit videos via Cognoa Research App Video analysts will access, review, and provide information via Video Analyst Portal
Module 3 - Healthcare Provider Assessment	Answers to questions on key developmental behaviors (by age group), provided by the child's healthcare provider.	Healthcare provider responses will be captured on a form via pen and paper. Study Staff data entry personnel will enter information from form into a study database.

The device evaluates the data inputs based on key developmental behaviors that are most indicative of autism and provides the following outputs -- Positive for Autism Spectrum Disorder (Positive ASD) or Negative for Autism Spectrum Disorder (Negative ASD). The device output will be recorded by Sponsor in a dedicated study data repository. It will not be shared with the referring HCP, caregivers, or specialist clinicians performing diagnosis and review.

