7.3 Exclusion Criteria

Subjects will be excluded from the study if they meet any of the following Exclusion Criteria:

- Subjects with a prior diagnosis of ASD rendered by a healthcare professional.
- Subjects with suspected auditory or visual hallucinations or with prior diagnosis of childhood onset schizophrenia.
- Subjects with deafness or blindness.
- Subjects with known physical impairments affecting their ability to use their hands.
- Subjects with major dysmorphic features or prenatal exposure to teratogens (such as fetal alcohol syndrome).
- Subjects with history, suspicion, or diagnosis of genetic conditions (such as Rett's Syndrome or Fragile X).
- Subjects with microcephaly.
- Subjects with history or prior diagnosis of epilepsy or seizures.
- Subjects with a history of neglect.
- Subjects with a history of brain malformation, injury or insult requiring interventions such as surgery or chronic medication.
- Subjects whose age on the date of enrollment is outside the target age range.
- Subjects or caregivers who have been previously enrolled in any Cognoa clinical study or survey.
- Subjects whose medical records had been included in any internal Cognoa training or validation sets.

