2.6 Mitigation of Bias

2.6.1 Verification bias:

No verification bias is expected to be present. All study participants will receive the reference standard diagnosis and be assessed by the device.

2.6.2 Selection bias:

No selection bias is expected to be present. The study enrollment criteria are set to match the intended indications for use of the device. Specifically, the parental level of concern for possible autism confirmed by the HCP and allowed age range are managed. For more details, refer to section *IV. Study Subjects of the Protocol*.

2.6.3 Spectrum bias:

No spectrum bias is expected to be present. The study design adopts open enrollment that is expected to enroll children from these relevant subgroups at the rates at which they are present in the target population:

- Children who are developing normally
- Children with ASD
- Children with other neurodevelopmental conditions such as ADHD, speech and language delay, etc.
- Children with both ASD and one or more other neurodevelopmental conditions

The proportions of children in the sample with these conditions are expected to match the proportions of children in the target population with these conditions, and the observed proportions will be reported.

2.6.4 Training bias:

No training bias is expected to be present. Every caregiver will undergo the device assessment only once, and all previous Cognoa users are excluded from the study. Therefore, no individual user will have the opportunity to change their ability with the device over the course of the study. Health Care Provider (HCP) users will be trained on using the device prior to the commencement of the study, in order to reduce the risk that a HCP changes how they use the device over the course of the study.

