3 STUDY POPULATION

The study population is intended to be representative of the population of children, aged between 18 months and 72 months, who visit their primary HCP for standard check-ups such as wellness checks and about whom the HCP or the caregiver has concern for developmental delay. For more details, refer to section 7. *Study Population* of the Protocol.

In the study population, we expect the prevalence of ASD to be higher than the prevalence of ASD in the general population. Based on prior investigations performed by Cognoa, Inc., we expect the prevalence of ASD in the study population to be approximately 24%.

We expect the study population to match the population of the United States in terms of race and ethnicity proportions.

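### SAP 2.6 says enrolment is open and matches the indications for use, but Protocol 7.3 excludes clinical groups that the intended use in Protocol 2 and the population in SAP 3 include, so device performance is not estimated for them

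*SAP*

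**What the plan says.** **Intended use.** Protocol 2 describes the device as an aid for children from 18 to under 72 months "who are at risk for developmental delays based on a parental or healthcare provider concern". It states no clinical exclusion.

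**Study population in the SAP.** SAP 3 says "The study population is intended to be representative of the population of children, aged between 18 months and 72 months", seen at routine primary care visits, "about whom the HCP or the caregiver has concern for developmental delay". That sentence also carries no clinical exclusion. The section then refers to Protocol 7 for detail.

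**Bias statements.** SAP 2.6.2 expects no selection bias, on the ground that "The study enrollment criteria are set to match the intended indications for use of the device". SAP 2.6.3 says "No spectrum bias is expected to be present. The study design adopts open enrollment". It lists four subgroups (normal development, ASD, other neurodevelopmental conditions, and ASD with another condition) whose sample proportions "are expected to match the proportions of children in the target population with these conditions".

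**Eligibility.** Protocol 7.3, repeated in the Protocol Summary, has 13 exclusions. They include "Subjects with history, suspicion, or diagnosis of genetic conditions" and "Subjects with deafness or blindness".

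**The concern.** A child with a seizure history, or in whom a genetic condition is merely suspected, can be of the right age and the subject of a developmental concern. That child is inside Protocol 2 and SAP 3 but cannot enter the trial. Enrolment is then not open in the sense SAP 2.6.3 needs, and the criteria do not match the indications.

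This matters because PPV and NPV form the composite primary endpoint and both depend on case mix. The no-result proportion, the other primary endpoint, can also vary with case mix. A reader who relies on SAP 2.6 and 3 would take a pass as applying to every child with a developmental concern, including groups in whom the device was never tested. The assumed match also enters the planning: SAP 5.4 takes its expected 6% positive, 63% negative and 31% no-result split from the intended population of use and applies it to the enrolled sample.

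**Working it through.** **Step 1: the plan's own figures.** From SAP 5.4, 725 × (1 − 0.25) = 543.75, or 544 completers. Taking 6%, 63% and 31% of 544 gives 33, 343 and 169, as in its table.
- Exact binomial: P(X ≥ 27 | n = 33, p = 0.90) = 95.8% (SAP: 96%). P(X ≥ 304 | n = 343, p = 0.92) = 98.9% (SAP: 99%).
- Lower 95% limits, p̂ − 1.96·√(p̂(1 − p̂)/n): 27/33 gives 68.7% and 304/343 gives 85.3%, as stated.

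These figures reproduce and are not in dispute here. They describe enrolled children only.

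**Step 2: which exclusions are at issue.** Four of the 13 are not contested. Prior ASD diagnosis, earlier Cognoa enrolment and use in training or validation data are ordinary validation safeguards, and the age limit agrees with Protocol 2. That leaves 13 − 4 = 9:
- deafness or blindness
- impaired hand use
- major dysmorphic features or teratogen exposure
- known or suspected genetic conditions
- microcephaly
- epilepsy or seizures
- neglect
- suspected hallucinations or childhood-onset schizophrenia
- brain malformation, injury or insult that required intervention

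**Step 3: set the sections side by side.**

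| Child of eligible age with a developmental concern and one of the nine conditions | Included? |
|---|---|
| Protocol 2, intended use | Yes |
| SAP 3, population sentence | Yes |
| Protocol 7.3 | No |
| Planned contribution to the 725 | 0 |

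The eligible population is therefore a strict subset of the intended-use population. None of the four subgroups in SAP 2.6.3 is itself excluded, but members of any of them who also have one of the nine conditions are. Their proportions would match the target population only if the excluded children divided among the four subgroups as the others do. The documents give no reason to expect that.

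**Step 4: can the effect be sized?** Let s be the excluded groups' share of device-positive (or device-negative) children, and PPVx and NPVx the values among them. Starting from the SAP's expected 90% and 92%:

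PPV_all = (1 − s) × 0.90 + s × PPVx; NPV_all = (1 − s) × 0.92 + s × NPVx.

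The documents give none of s, PPVx or NPVx, so every row below is an assumption.

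| s | PPVx / NPVx | PPV_all | NPV_all |
|---|---|---|---|
| 5% | 65% / 85% | 0.855 + 0.0325 = 88.75% | 0.874 + 0.0425 = 91.65% |
| 10% | 50% / 75% | 0.81 + 0.05 = 86.0% | 0.828 + 0.075 = 90.3% |
| 20% | 40% / 70% | 0.72 + 0.08 = 80.0% | 0.736 + 0.14 = 87.6% |
| 20% | 100% / 100% (ceiling) | 0.72 + 0.20 = 92.0% | 0.736 + 0.20 = 93.6% |

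The share at which NPV_all falls to 85% is (0.92 − 0.85)/(0.92 − NPVx): 41% if NPVx is 75%, 32% if 70%, and 17% if 50%. For PPV_all to fall to 65%, (0.90 − 0.65)/(0.90 − PPVx) gives 62.5% if PPVx is 50% and 50% if 40%.

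**Step 5: direction.** An NPVx of 75% means that 25% of device-negative excluded children have ASD, more than the 24% prevalence SAP 3 expects in the whole study population. With an informative device, ASD prevalence among the classified excluded children would have to be higher still. If these groups are mostly non-ASD delay, NPV there could exceed 92%. The device may also abstain more often in them, which would change s. The sign of the difference is open.

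**The case against.** The strongest reply is that the SAP claims less than it first appears to. SAP 2.6.2 goes on to name only level of concern and age as the features managed. The proportions statement in SAP 2.6.3 covers four listed subgroups, none of which is excluded. SAP 3 points to Protocol 7, where the exclusions are in plain view. Protocol 3 compares device output with the reference standard without citing the intended use, and Protocol 4.1 sets the PPV/NPV composite, sensitivity and specificity in the overall study population. Excluding such groups is a disclosed design choice, and any final labelling is not among the documents.

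Much of this stands. The objective and endpoints are already confined to enrolled children, and no estimator or decision rule is wrong. It does not rescue SAP 2.6. If the target population means whoever Protocol 7 admits, the statement that the sample matches it is circular, and Protocol 2 is still broader. Naming age and concern as the managed features confirms that the exclusion list was left out of account. Disclosing exclusions in one document does not make a statement of open enrolment in another correct.

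**Conclusion.** The contradiction is in the current text and needs no assumed figure: nine clinical groups fall inside Protocol 2 and the population sentence of SAP 3, are barred by Protocol 7.3, and supply 0 of 725 planned subjects. PPV, NPV, sensitivity, specificity and the no-result rate are not estimated for them. SAP 2.6.2 and 2.6.3 should not say otherwise. The finding assumes only that eligibility is applied as written and that such children can prompt a developmental concern.

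A reader might infer three stronger things that the documents do not support.
- **That the excluded children are harder to classify, so the trial will overstate accuracy.** Nothing in the documents says so, and Step 4 gives a shift in either direction depending on the inputs chosen.
- **That the objective goes unanswered or the primary endpoint is invalid.** Protocol 3 and 4.1 do not tie either to the wider intended use, and the trial remains informative for the enrolled population.
- **That the exclusions themselves are wrong.** The documents give no basis for that. The fault lies in what the SAP says about the exclusions' effect.

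**What to change.** 1. In SAP 2.6.2, 2.6.3 and 3, replace the statements that the criteria match the indications, that enrolment is open, and that no selection or spectrum bias is expected. Suggested text: *The target population is children who meet Protocol 7.2 and none of the exclusions in Protocol 7.3. PPV, NPV, sensitivity, specificity and the no-result proportion apply to that population only.*
2. Reconcile the intended-use statement in Protocol 2 with Protocol 7.3. Protocol 3 needs no change.
3. Report screen failures by 7.3 criterion, but only where eligibility answers were retained. Protocol 6 has caregivers answer eligibility questions, yet Protocol 7.4 assigns an ID only to eligible subjects and the repository list in Protocol 8 names no screening data. With 600 subjects already enrolled at the SAP's date, the table would be largely retrospective. It would not give the full excluded share, since providers may never mention the study to families they expect to be ineligible.

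The cost is an edit to both documents and, where data exist, one table. Eligibility, conduct, sample size and analysis are unchanged. The downside is that the supported claim is narrower.

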3 STUDY POPULATION

The study population is intended to be representative of the population of children, aged between 18 months and 72 months, who visit their primary HCP for standard check-ups such as wellness checks and about whom the HCP or the caregiver has concern for developmental delay. For more details, refer to section 7. *Study Population* of the Protocol.

In the study population, we expect the prevalence of ASD to be higher than the prevalence of ASD in the general population. Based on prior investigations performed by Cognoa, Inc., we expect the prevalence of ASD in the study population to be approximately 24%.

We expect the study population to match the population of the United States in terms of race and ethnicity proportions.

4 STATISTICAL PRINCIPLES

4.1 Confidence Intervals and P-values

In the analysis of the primary endpoints, 3 two-sided confidence intervals will be computed. Each endpoint will be evaluated at a 95% confidence level. The analysis of the first primary endpoint includes the computation of two distinct confidence intervals and two minimally

acceptable values that must be surpassed for the endpoint's performance goal to be considered met. In order to achieve a joint 95% confidence level for the entire endpoint, each of the two confidence intervals will be computed with a 95% confidence level and the lower end of the interval checked against the minimum acceptable value. This ensures a joint 95% confidence level on the conclusion that both measures evaluated in the first primary endpoint meet their minimum acceptable values. The second primary endpoint consists of a single confidence interval, which will also be 95% and two-sided.

All other confidence intervals presented will also be 95% and two-sided.

For full specifications of the analysis of the endpoints, refer to section 5.1 *Analysis Methods* of this document.

4.2 Analysis Populations

The analysis will be performed on an intention-to-diagnose basis [2]. The analysis population will include all participants. For details on how dropouts, missing data, and protocol noncompliance will be analyzed, refer to section 5.2 *Handling of Dropouts and Missing Data* of this document.

5 STATISTICAL ANALYSIS METHODOLOGY

The response of the device is categorical. It reports that a subject is Positive for ASD ("+ASD") or Negative for ASD ("-ASD"). Additionally, the device has the option to "abstain" from classification when the sample is not evaluable ("no result").

The following contingency table describes all the possible combinations of the device diagnostic output and clinician panel determination (the reference standard). The nomenclature outlined here is used in the following sections to specify the metrics used in the evaluation of the endpoints.

		Clinician Panel Determination (Reference Standard)	
		Positive ASD	Negative ASD
Device Diagnostic Output	+ASD	True Positive (TP)	False Positive (FP)
	-ASD	False Negative (FN)	True Negative (TN)
	No Result	No Result Positive (NRP)	No Result Negative (NRN)

5.1 Analysis Methods

5.1.1 Analysis of the Primary Endpoints

The Predictive Values of the device outcomes will be computed as:

Device Outcome	Probability of Interest	Computation	Minimally Acceptable Value
+ASD	$PPV = P(\text{Ref}=\text{+ASD} \text{Device}=\text{+ASD})$	$\frac{TP}{TP + FP}$	0.65
-ASD	$NPV = P(\text{Ref}=\text{-ASD} \text{Device}=\text{-ASD})$	$\frac{TN}{TN + FN}$	0.85

Two-sided 95% confidence intervals of each metric will be computed and reported. If both confidence intervals lie entirely above the minimally acceptable values, the endpoint will be considered to be met.

The proportion of all subjects who receive a "no result" outcome will be computed as:

Device Outcome	Probability of Interest	Computation
no result	$P(\text{Device}=\text{no result})$	$\frac{NRP + NRN}{\Sigma all}$

A two-sided 95% confidence interval around the metric will be computed and reported.

Note that the values used in the computation of the metrics used in the analysis of the primary endpoints are only defined for data-complete subjects. Therefore, in the analysis of the primary endpoints only subjects who complete the device assessment will be included. Additional analyses will be performed on subjects who drop out, as specified in section 5.2 *Handling of Dropouts and Missing Data* of this document.

5.1.2 Analysis of the Secondary Endpoints

The Sensitivity and Specificity of the device will be computed as:

Metric	Probability of Interest	Computation
ASD Sensitivity	$P(\text{Cognoa}=\text{+ASD} \mid \text{Ref}=\text{+ASD})$	$\frac{TP}{TP + FN}$
ASD Specificity	$P(\text{Cognoa}=\text{-ASD} \mid \text{Ref}=\text{-ASD})$	$\frac{TN}{TN + FP}$

Two-sided 95% confidence intervals of each metric will be computed and reported.

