Term	Definition
Cognoa Research App	A smartphone-based app that describes the Cognoa device, provides guidance on and access to assessments and video software, and serves as a collection mechanism for assessments and videos.
Coverage	Proportion of a data set for which a classifier makes a prediction.
Diagnostic Output	Output from the Cognoa Device that is used as part of an overall diagnosis decision.
Dropout	After consenting to participation in trial (and therefore enrolling), a study subject discontinues participation in the trial (e.g., due to lack of interest, medical condition, adverse event). Dropout may simply be lost to follow up.
DSM-5	Diagnostic and Statistical Manual of Mental Disorders, Fifth Edition; a guide to clinicians for diagnosis of neurobehavioral and psychiatric disorders.
Endpoint	Key outcome measure in a clinical study.
Feature	Individual measurable property or characteristic of an observation.
Futility	Situation in which proceeding further with a trial is not safe, feasible, or warranted from a statistical perspective. Studies can be stopped early due to unacceptable safety or risk/benefit profile, inability to recruit or perform study procedures, overwhelming early efficacy, or statistical impossibility of achieving endpoint(s).
HCP	Healthcare provider.
IC / ICF	Informed consent / Informed consent form.
IRB	Institutional review board.
Negative Predictive Value	Probability that a child identified by the device as Negative for ASD truly doesn't have ASD $NPV = (\text{True Negative}) / (\text{True Negative} + \text{False Negative})$
Positive Predictive Value	Probability that a child identified by the device as Positive for ASD truly has ASD $PPV = (\text{True Positive}) / (\text{True Positive} + \text{False Positive})$
Prevalence	Number of cases in a defined population at a single point in time, regardless of when they first developed the condition. $\text{Prevalence} = (\# \text{ of cases in sample with condition}) / (\text{total } \# \text{ of cases in sample})$
Screening tool	A tool used in assist in clinical triage.

Term	Definition
Sensitivity	
Measure of the proportion of children truly having ASD who are correctly identified by the device as Positive for ASD (or True positive rate).
 $\text{Sensitivity} = (\text{True Positive}) / (\text{True Positive} + \text{False Negative})$

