2.3 Secondary Endpoints

1. Sensitivity to ASD of the device
2. Specificity to ASD of the device

These secondary endpoints will be analyzed by reporting the estimate of the specified metric as well as its 95% confidence interval. The trial will not be powered for rigorous statistical tests of the secondary endpoints. For full specifications of the analysis of the secondary endpoints, refer to section 5.1 *Analysis Methods* of this document.

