5.1.3 Additional Analyses

Additionally, in order to quantify the makeup of the group of subjects for whom the Device provides no result, the following proportions will be computed:

Metric	Probability of Interest	Computation
Proportion of "no result" with +ASD	$P(\text{Ref}=\text{+ASD} \mid \text{Cognoa}=\text{no result})$	$\frac{NRP}{NRP + NRN}$
Proportion of "no result" with -ASD	$P(\text{Ref}=\text{-ASD} \mid \text{Cognoa}=\text{no result})$	$\frac{NRN}{NRP + NRN}$

Two-sided 95% confidence intervals of each metric will be computed and reported.

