5.4 Sample size and power analysis

Cognoa plans to enroll 725 subjects in total. In prior studies of the device, dropout was identified as a potentially significant risk. Consequently, with a dropout rate of up to 25%, this total enrollment will ensure a minimum of 525 study completers.

In the intended population of use for the Cognoa device, based on prior studies with the device, we expect approximately 6% of subjects to be labeled +ASD by the device, 63% to be labeled -ASD, and 31% to get no result. With 525 study completers, we would expect approximately 32 to be labeled +ASD by the device, approximately 331 to be labeled -ASD, and approximately 163 to get no result. The following table summarizes these expected enrollment numbers.

Category	Expected Number of Subjects
Total Enrollment	725
Study Completers	544
Cognoa Test +ASD	33
Cognoa Test -ASD	343
Cognoa Test No Result	169

With these expected numbers of subjects, if 27 or more of the anticipated 33 Cognoa test positive subjects are found to truly be positive according to the reference standard then the PPV 95% confidence interval will have lower bound 68.7% and the primary endpoint's PPV performance goal will be met. Similarly, if 304 or more of the anticipated 343 Cognoa test negative subjects are found to truly be negative according to the reference standard then the NPV 95% confidence interval will have lower bound 85.3% and the primary endpoint's NPV performance goal will be met.

Cognoa expects the device to demonstrate PPV greater than 90% and NPV greater than 92%. With 90% PPV, there is a 96% chance that 27 or more of the anticipated 33 Cognoa test positive subjects will be found to truly be positive according to the reference standard. With 92% NPV, there is a 99% chance that 304 or more of the anticipated 343 Cognoa test negative subjects will be found to truly be negative according to the reference standard.

Therefore, the enrollment plan outlined above has greater than 80% power at a 95% confidence level.

Additionally, with the expected minimum 544 study completers we would expect approximately 169 to get no result from the Cognoa device and a "no result" proportion 95% confidence interval with range no greater than $\pm 7.5\%$.

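### SAP 5.1.2 defines sensitivity and specificity over all children in each reference group, but its formulas leave out children with no device result and do not say so

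*SAP*

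**What the plan says.** SAP section 5 allows three device outputs: positive, negative and no result. Its contingency table crosses these with the reference standard, so the reference-positive column holds TP, FN and a third cell, "No Result Positive (NRP"). The reference-negative column likewise holds TN, FP and NRN.

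SAP section 5.1.2 begins "The Sensitivity and Specificity of the device will be computed as" and sets a probability beside a formula for each metric:

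- Sensitivity: the probability of a +ASD output given reference-positive, computed as TP/(TP+FN).
- Specificity: the probability of a -ASD output given reference-negative, computed as TN/(TN+FP).

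The protocol glossary uses the same two formulas. It defines sensitivity in words as "Measure of the proportion of children truly having ASD who are correctly identified by the device as Positive for ASD", with no restriction to children who receive a result. Protocol section 2 says the device "provides the following outputs -- Positive for Autism Spectrum Disorder (Positive ASD) or Negative for Autism Spectrum Disorder (Negative ASD"), although protocol section 4.1 makes the no-result proportion a primary endpoint. Section 4.1 also sets both secondary endpoints for the whole study population.

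No-result children are reported elsewhere. SAP 5.1.1 gives their overall proportion, and SAP 5.1.3 adds their split by reference diagnosis, "in order to quantify the makeup of the group of subjects for whom the Device provides no result". On the standing of sensitivity and specificity, SAP 2.3 says "The trial will not be powered for rigorous statistical tests of the secondary endpoints".

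**The concern.** With two outputs, the formula and the stated probability are the same thing. With three they differ, because a child with ASD who gets no result belongs to the reference-positive group but not to TP+FN. What 5.1.2 computes is the probability of a +ASD output given ASD and given a determinate result. That second condition is written nowhere.

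The nearest restriction is the note in SAP 5.1.1. It concerns the primary endpoints and limits them to children who complete the device assessment. No-result children can meet that test: SAP 5.4 counts 169 of them among 544 completers. The intention-to-diagnose basis in SAP 4.2 and 5.2 also points towards the wider denominator.

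For these two endpoints, the estimate with its confidence interval is the whole planned analysis, so its meaning has to be right. A reader who takes the probability column at face value would believe the device flags a much larger share of children with ASD than it does. The formula's value also depends on which children get no result: turning false negatives into no-results raises it, although no further child with ASD is identified.

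**Working it through.** **The plan's own figures.** The SAP states no expected sensitivity or specificity, so the check starts with the figures that supply the inputs.

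- 725 × 0.75 = 543.75, or 544 completers. Applying 6/63/31% gives 33, 343 and 169, as tabulated in SAP 5.4.
- The chance of at least 27 of 33 at PPV 90% is 95.8% (SAP: 96%). The chance of at least 304 of 343 at NPV 92% is 98.9% (SAP: 99%). Both reproduce.

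**Inputs.**

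- Device outputs, SAP 5.4: "we expect approximately 6% of subjects to be labeled +ASD by the device, 63% to be labeled -ASD, and 31% to get no result".
- PPV 90% and NPV 92%, SAP 5.4. The SAP expects to exceed both.
- ASD prevalence about 24%, SAP section 3.
- Assumption: these all hold together among completers.

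**Cells, as fractions of completers.**

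- TP = 0.06 × 0.90 = 0.0540; FP = 0.06 × 0.10 = 0.0060
- FN = 0.63 × 0.08 = 0.0504; TN = 0.63 × 0.92 = 0.5796
- NRP = 0.24 − 0.0540 − 0.0504 = 0.1356
- NRN = 0.31 − 0.1356 = 0.1744

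**Formula against stated probability.**

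| Metric | SAP formula | Stated probability |
|---|---|---|
| Sensitivity | 0.0540/0.1044 = 51.7% | 0.0540/0.24 = 22.5% |
| Specificity | 0.5796/0.5856 = 99.0% | 0.5796/0.76 = 76.3% |

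**Precision at 544 completers.** Rounded expected counts are TP 29, FN 27, NRP 74, TN 315, FP 3 and NRN 95 (total 543 through rounding). The SAP names no interval method; exact intervals are assumed.

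| Metric | SAP formula, 95% CI | Stated probability, 95% CI |
|---|---|---|
| Sensitivity | 29/56: 38.0–65.3% | 29/130: 15.5–30.4% |
| Specificity | 315/318: 97.3–99.8% | 315/413: 71.9–80.3% |

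**No-result share of each reference group.** Reference-positive: 0.1356/0.24 = 56.5%. Reference-negative: 0.1744/0.76 = 22.9%. False positives are 0.0060/0.76 = 0.8% of reference-negatives.

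**Sensitivity of these figures to the inputs.**

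- PPV 90–100% and NPV 92–98% (upper ends assumed), prevalence 24%: formula sensitivity is 51.7–82.6% and the stated probability 22.5–25.0%, the ceiling being 6%/24%. Formula specificity is 99.0–100% and the stated probability 76.3–81.2%.
- Prevalence 20–30% (assumed range), PPV 90%, NPV 92%: formula sensitivity stays at 51.7%, while the stated probability runs from 0.0540/0.20 = 27.0% down to 0.0540/0.30 = 18.0%.
- The two versions of sensitivity agree only if NRP = 0, that is at prevalence 0.0540 + 0.0504 = 10.4%.

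**Dependence on who gets no result.** Hold the output rates, prevalence and PPV 90% fixed, and raise NPV to 98%. FN falls to 0.63 × 0.02 = 0.0126 and NRP rises to 0.24 − 0.0540 − 0.0126 = 0.1734, so 3.8% of all children move from FN to NRP. Formula sensitivity becomes 0.0540/0.0666 = 81.1%. The stated probability is still 0.0540/0.24 = 22.5%.

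**The case against.** The strongest reply is that this is loose notation. The formulas are printed, all six cells are defined, and the protocol and SAP agree on the computation, so no analyst could compute anything else. Accuracy where a prediction is made, reported together with coverage, is a usual presentation for a classifier that may abstain. The glossary defines coverage in that sense and SAP 1.2 lists it beside sensitivity and specificity. The no-result proportion is a primary endpoint, and 5.1.3 gives its make-up with confidence intervals. A short label would then be enough.

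Much of this stands. TP/(TP+FN) is a legitimate metric, what will be computed is not in doubt, and the all-children values can be derived from the tabulated cells. But the plan still names a different quantity from the one it computes. SAP 5.1.3 conditions on no result rather than on reference status, and no all-children estimate or interval is planned. A label alone would cure the mismatch. It would still leave the protocol's whole-population endpoint without a direct estimate.

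Cautions about the size are also fair. NRP is a residual from inputs that the SAP attributes to different prior work; it implies 0.1356/0.31 = 44% ASD among no-results, a figure the SAP does not give. At 20% prevalence the ratio is 51.7/27.0 = 1.9, not above two. The non-overlapping intervals belong to two different quantities and test nothing; they show only that sampling error would not hide the difference. The NPV 98% case is an illustration.

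**Conclusion.** The concern holds. Under the SAP's own three-row table, the 5.1.2 formulas do not estimate the probabilities printed beside them; they do so only among children with a determinate result, and that condition is unstated. On the planning inputs the gap is about 29 percentage points for sensitivity and 23 for specificity. These sizes rest on combining the SAP's output rates, predictive values and prevalence in one completer population, and they would change with the observed data. The mismatch itself rests on no assumption beyond some children receiving no result. PPV and NPV condition on the device output, so the primary test is untouched, and no success decision depends on the secondary endpoints. It should still be corrected, because a reader could misread the reported figures badly.

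**What to change.** Amend SAP 5.1.2 before the blind is broken:

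1. Report TP/(TP+FN+NRP) and TN/(TN+FP+NRN), each with a two-sided 95% confidence interval, as the estimates of the probabilities now stated.
2. Keep TP/(TP+FN) and TN/(TN+FP) beside them, labelled as applying to subjects with a determinate device result, and write their probabilities as conditional on the output not being no result.
3. Report the no-result share of each reference group, NRP/(TP+FN+NRP) and NRN/(TN+FP+NRN), so that no-results are not read as wrong classifications.

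The protocol glossary should carry the same distinction.

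The cost is one label, two metrics with intervals and two shares, all from cells already tabulated. There is no new data collection and no effect on sample size or the primary test. The all-children figures will look less favourable. Without the third item, specificity near 76% could be misread as a false-positive rate near 24%, when expected false positives are 0.8% of reference-negatives.
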